Individuals included in this project will be adults (18 years or older) who have experienced a TBI. Participants with any of the following will be excluded from the study: imminent risk of psychiatric hospitalization, imminent danger of hurting themselves or others, or active substance abuse (e.g., intoxicated at intake), as judged by the investigators.

The proposed study will evaluate the benefits of the Resilience and Adjustment Intervention for improving resilience and emotional well-being after TBI. The study is a two-arm randomized controlled trial comparing the benefits of a basic resilience-building intervention (RAI) with an expanded, patient-centered resilience intervention (RAI+).

We expect to enroll approximately 154 participants over the course of the grant. TBI often causes physical and mental disabilities. Thus, adults with physical and/or mental disabilities will be included. Pregnant women will also be enrolled, as there is no indication of additional risk to mother or fetus. Individuals in the following special classes will **not** be studied: children, prisoners, and institutionalized individuals.

(2) Sources of Materials: Identify the sources of research material obtained from identifiable living human subjects in the form of specimens, records, or data. Indicate whether the material or data will be obtained specifically for research purposes or whether use will be made of existing specimens, records, or data.

Research materials will be comprised of data obtained through questionnaires, interviews, and medical records review. Information will be obtained specifically for the research purposes of the project.

(3) Recruitment and Informed Consent: Describe plans for the recruitment of subjects and the consent procedures to be followed. Include the circumstances under which consent will be sought and obtained, who will seek it, the nature of the information to be provided to prospective subjects, and the method of documenting consent. State if the Institutional Review Board (IRB) has authorized a modification or waiver of the elements of consent or the requirement for documentation of consent.

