success of the proposed research program will allow for the "scaling up" of the RAI in hopes that

the evidence-based intervention will be widely adopted in practice.

D2. Sample

Information regarding inclusion and exclusion criteria, enrollment rate, and participant incentives is provided herein. Recruitment information is provided in the *Procedure* section.

Inclusion criteria: Individuals 18 years of age and older with mild, moderate, or severe TBI who are able to understand and provide consent will be eligible to participate. The standard TBIMS brain injury definition will be used: damage to brain tissue caused by an external mechanical force as evidenced by loss of consciousness due to brain trauma, post-traumatic amnesia (PTA), skull

fracture, or objective neurological findings that can be reasonably attributed to TBI on physical examination or mental status examination. Since there is no reason to believe that treatment effectiveness varies with chronicity, no maximum has been set for time postinjury.

Exclusion criteria: Active substance abusers (e.g., intoxicated at arrival to intake), individuals at imminent risk of psychiatric hospitalization or in imminent danger of hurting themselves or others, as judged by the investigators, will be excluded from the study. Records will be kept indicating the number and type of exclusions. The data will be evaluated to help ascertain the representativeness of the final sample.

Enrollment rate: Considering the inclusion and exclusion criteria and past research experience at VCUHS, average monthly accrual rates are estimated to range between 3-4 participants. Considering potential attrition rates (e.g., 10%), we conservatively estimate an accrual rate of no less than 154 participants over the 46-month enrollment period. As noted in the *Data Analysis* section, power analyses indicate our anticipated sample size exceeds recommended minimums. **Participant incentives:** Participants will be provided therapy, educational materials, and referral services at no cost. Each participant will receive up to a total of \$140. Individuals will receive \$25 for completing each of the first two assessments (pre- and post-treatment) and \$30 each for the latter three (pre- and post-booster, and long-term follow-up). For participants traveling more than 60 miles roundtrip, funds will be provided to offset travel costs (IRS mileage rate of 19 cents per mile driven).

D3. Intervention

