Statistical Methods: A linear mixed-effects model will be used to model the CD-RISC scores over time for the RAI and RAI+ groups. The model will include fixed-effects for time at RAI+Booster initiation, conclusion, and long-term follow-up (e.g. 5, 6, and 11 months), group (RAI or RAI+) and the interaction between group and time. The model will also adjust for fixed-effects for injury severity, time postinjury, and education. Within-subject correlations in the CD-RISC scores over time will be modeled using a spatial power covariance pattern structure. Specific contrast statements will be used to test for a difference in the CD-RISC change scores between the treatment groups at both RAI+Booster initiation and conclusion as well as RAI+Booster initiation and long-term follow-up at a significance level of .05.

Power Analysis: Data obtained by our group indicated that the mean CD-RISC increased from a baseline value of 21.1 units to a mean of 28.4 units post-treatment (Difference=7.3), followed by a decline to 25.5 at the 3-month follow-up (Difference=2.9), with a standard deviation (SD) of the change score equal to 5.0. Considering a conservative SD of 6.0, this study will require 138 participants (n=69 per group) using a two-sample t-test performed at the 0.05 significance level to achieve 80% power. This effect translates to an effect size d=2.9/6.0=0.48, which is typically considered a moderate effect size.

Hypothesis 2: Participants in the RAI+ group will show better adjustment and lower levels of emotional distress as compared to persons in the standard RAI group.

Statistical Methods: Separate mixed-effects models, similar to that outlined in the methods for Hypothesis 1, will be used to model the responses for the MPAI-4 Adjustment Index and the BSI-18 GSI scores over time for each group. Specific contrast statements will be used to test the hypotheses of interest, each assuming a significance level of .05. Using a similar 40% decrease between the baseline to post-treatment values observed in our pilot study, we would expect the RAI+ to ameliorate declines in the MPAI-4 Adjustment and BSI-18 GSI scores by 1.7 and 2.6 points, respectively. Considering a conservative SD of 7.0, the 138 participants enrolled would provide power of 29% and 58% for the two outcomes, if analyzed by a two-sample t-test at the 0.05 level.

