Hypothesis 3: Participants in the RAI+ group will report greater abilities in the areas of problem solving, communication, and stress management relative to persons in the standard RAI group. **Statistical Methods:** Two additional mixed-effect models, similar to the first three, will be used to

model the MPAI-4 Ability scores and the 13-Item Stress Test scores over time for each group. Again, a specific contrast statement will be used to test the hypothesis of interest at a significance level of α = .05. In a similar fashion to Hypothesis 2, a 40% decrease between the observed baseline to post-treatment values yields differences of 1.6 and 0.9 for the MPAI-4 Ability Index and the 13-Item Stress Test. Considering a conservative SD of 7.0 and 2.0, respectively, the 138 participants enrolled would provide power of 27% and 75% for the two outcomes, if analyzed by a two-sample t-test at the 0.05 level.

Hypothesis 4 (exploratory): A participant's demographic, lifestyle, injury, and treatment response information will be predictive of maintenance ability.

Statistical Methods: Separate linear regression models will be used to determine the relationship between each of the demographic, lifestyle, injury, and initial RAI response characteristics and both the change in the 5 and 6 month CD-RISC scores, as well as the change in the 5 and 11 month CD-RISC scores. Assuming 69 participants in the RAI group complete the study and 8 predictor variables are in the linear regression model, this analysis will have 80% power to detect effect sizes of f^2 =0.12, which is considered a moderate effect size.

Power analyses relating to the primary hypothesis indicate minimum group sizes of 69 participants.

If we allow for a maximum of 10% attrition, then an additional 8 individuals per treatment group

(16 individuals total) should be recruited (138/(1-0.1)-138 = 15.3) for a total sample size of 154.

F. Feasibility F1. Project Staff

Personnel effort levels are based on thorough consideration of our prior experience conducting

similar projects. Following is information on responsibilities of personnel allocating >5% effort:

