- 3. * Provide justification for the sample size by explaining how you arrived at the expected number of participants and why this number is adequate for answering the research questions: Power analyses relating to the primary hypothesis indicate minimum group sizes of 69 participants. If we allow for a maximum of 28% attrition, then an additional 27 individuals per treatment group (54 individuals total) should be recruited (138/(1-0.28)-138 = 53.67), yielding a sample size of 192.
- 4. * List the study inclusion criteria:

Individuals meeting the following:

Eighteen years of age and older.

Mild, moderate, or severe TBI defined as: damage to brain tissue caused by an external mechanical force as evidenced by loss of consciousness due to brain trauma, post-traumatic amnesia (PTA), skull fracture, or objective neurological findings that can be reasonably attributed to TBI on physical examination or mental status examination.

At least 3 months post-TBI.

Since there is no reason to believe that treatment effectiveness varies with chronicity, no maximum has been set for time postinjury.

5. * List the study exclusion criteria:

Active substance abusers (e.g., intoxicated at arrival to intake).

Individuals at imminent risk of psychiatric hospitalization, or in imminent danger of hurting themselves or others, as judged by the investigators, will be excluded from the study.

6. * Will individuals with limited English proficiency be included in or excluded from this research?

→ Included

- C Excluded safety concerns if participants are unable to communicate with the study team
- Excluded instruments/measures only validated in English
- Excluded no prospect of direct benefit to individual participants
- Excluded minimal risk study

 $oldsymbol{\gamma}$ Excluded - lack of budget/resources for translation and interpretation [provide an explanation in next question]

- Excluded other reason [provide an explanation in next question]
- 7. Justify the inclusion and exclusion criteria if you are either targeting, or excluding, a particular segment of the population / community. Provide a description of the group/organization/community and provide a rationale. Individuals with limited English proficiency are excluded, as this is a minimal risk study. Further, the intervention involves working with an English-speaking interventionist and use of measures that have only been validated in the English language.

Background, Rationale & Goals Section Complete

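### Accrual of 3–4 a month for 46 months gives 138–184 enrolled, so 154 is attainable but is not a floor, and no stated rate or period supports the later target of 192

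*Combined protocol and SAP*

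**What the plan says.** The grant application, site-specific project, D2. Sample (Enrollment rate), says that "average monthly accrual rates are estimated to range between 3-4 participants". It then mentions attrition, with 10% as an example, and concludes that "we conservatively estimate an accrual rate of no less than 154 participants over the 46-month enrollment period". The next sentence says the anticipated sample is above the minimum from the power analysis.

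The Human Subjects narrative for the same project treats 154 as the number enrolled: "We expect to enroll approximately 154 participants over the course of the grant". Section E. Data Analysis shows where the figure comes from. Under Hypothesis 1, "this study will require 138 participants (n=69 per group) using a two-sample t-test performed at the 0.05 significance level to achieve 80% power", with "effect size d=2.9/6.0=0.48". The closing paragraph of that section adds an allowance for loss: "16 individuals total) should be recruited (138/(1-0.1)-138 = 15.3) for a total sample size of 154".

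The IRB form, Study Population item 3, keeps the 69 per group but changes the allowance: "If we allow for a maximum of 28% attrition", 27 more are needed per group, giving 192. Item 1 of the same page also enters 192 as the maximum number of individuals. The IRB form gives no accrual rate and no enrollment period.

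**The concern.** A figure offered as a conservative minimum should hold at the low end of the range it is drawn from. Here the low end is 138, and 154 is the recruitment requirement from Section E presented as though it were the expected minimum yield. The reassurance that the sample is above the power minimum depends on it.

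When the requirement rose to 192, the feasibility statement was not revisited in the IRB form. The figure is also used in running the study. The Plan of Evaluation makes quarterly enrollment against the project's specified minimum a performance measure, and the Data and Safety Monitoring Plan requires monthly accrual review. A study recruiting steadily at 3 a month would be within its forecast and still finish below both 154 and 192.

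**Working it through.** **Inputs.** Rate 3–4 a month, 46 months and 10% attrition (grant, D2). Completers required 138, d = 2.9/6.0, significance level 0.05, 80% power (grant, Section E, Hypothesis 1). Maximum attrition 28% and target 192 (IRB form, Study Population item 3). The plan does not say whether the test is one- or two-sided; two-sided is assumed.

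**The plan's sample sizes reproduce.**
- A two-sample t-test at 80% power needs 69.1 per group for d = 0.48 and 68.2 for d = 2.9/6.0 = 0.483. The stated 69 per group, 138 in total, is right.
- 138/(1 − 0.10) = 153.3, stated as 154.
- 138/(1 − 0.28) = 191.7, stated as 192.

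**The accrual floor does not reproduce.** Enrolled = rate × months.
- 3 × 46 = 138, which is 16 below 154.
- 3.5 × 46 = 161.
- 4 × 46 = 184, which is 8 below 192.

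**What each target requires.**
- 154/46 = 3.35 a month, or 154/3 = 51.3 months at 3 a month.
- 192/46 = 4.17 a month, or 192/4 = 48 months at 4 a month, or 192/3 = 64 months at 3 a month.

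**Completers and power.** Completers = enrolled × (1 − attrition). Power is for a two-sample t-test on completers with d = 2.9/6.0.

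| Enrolled | Rate over 46 months | Completers (power), 10% attrition | Completers (power), 28% attrition |
|---|---|---|---|
| 138 | 3.00 | 124 (76%) | 99 (66%) |
| 154 | 3.35 | 139 (81%) | 111 (71%) |
| 184 | 4.00 | 166 (87%) | 132 (79%) |
| 192 | 4.17 | 173 (88%) | 138 (81%) |

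At 10% attrition the requirement of 138 completers is met from about 3.35 a month upwards. At 28% it is not met anywhere in the 3–4 range, although 4 a month comes within about six people.

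**Room in the timetable.** The two-month start-up (D6. Procedure) plus 46 months ends at month 48, which matches the enrollment blocks in the project work plan. The last participant then has seven weeks of treatment (about 1.6 months) and an assessment nine months after treatment: 48 + 1.6 + 9 = 58.6, in a 60-month project. Two further months of enrollment would give 50 + 1.6 + 9 = 60.6.

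**The case against.** The strongest defence is that 3–4 a month is already net of loss. Then 3 × 46 = 138 is the number retained, which is exactly the requirement, and 138/0.9 = 153.3 gives 154 to enroll. On the same basis the top end is 184/0.9 = 204, and 192 is within reach. The attrition remark sits between the rate and the 154, and the Feasibility section bases its accrual numbers on past data collection rates, so the reading is not absurd. It is strained, though. The paragraph calls both figures accrual, the Human Subjects narrative and Section E treat 154 as the number enrolled or recruited, and attrition cannot raise the number accrued. If the net reading was intended, the text has to say so.

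Other objections limit the point and stand:
- **154 is attainable.** It lies below the midpoint of 161. A reader might infer that the rate cannot deliver it, but only its status as a floor fails. The monthly figures also look rounded: the caregiver module pairs two a month with 26 a year, which is 26/12 = 2.17.
- **192 is not shown to be out of reach.** A reader might infer that it is by joining the grant's rate and 46 months to the later IRB form. That form restates neither, and the gap at 4 a month is 8 people or two months.
- **28% is a stated maximum.** A reader might take 66–79% as the plan's power. The 66% combines the lowest rate, the highest attrition and the conservative SD of 6.0. With the SD of 5.0 that the grant reports, the same 99 completers give about 82%. The primary analysis is also a mixed model that can use partial data, whereas these figures come from a completers-only t-test.
- **Low accrual is anticipated.** The Feasibility section lists responses to it, and accrual is reviewed monthly. This reduces the practical risk but does not correct the stated minimum.

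**Conclusion.** The point holds in a limited form. On the grant's own rate and period, expected enrollment is 138–184, and 154 is a value inside that range rather than its minimum. At the low end with 10% attrition the study would have about 124 completers and about 76% power, so the claim that the sample is above the power minimum is true only from about 3.35 a month.

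For 192 the conclusion is conditional. If 3–4 a month and 46 months still apply, the target needs 4.17 a month, or 48 months at 4 a month, slightly above what was forecast. At the maximum 28% attrition, 4 a month loses almost nothing (79% against 80%), and the 66% at 3 a month is a worst case.

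This rests on reading accrual as enrollment, on a two-sided test, and on no revised rate or period existing in files that the IRB form lists but that are not reproduced here. The sample sizes of 138, 154 and 192 are correct as requirements.

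**What to change.** In the grant's Enrollment rate paragraph, or in a dated note to it:
1. State expected enrollment as 138–184 over 46 months at 3–4 a month. If the rate was meant net of attrition, say so and give the gross rate.
2. Replace the floor of 154 with the rate it requires, about 3.35 a month.
3. Limit the claim that the sample is above the power minimum to accrual of about 3.35 a month or more at 10% attrition.

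In the IRB form, Study Population item 3, state the accrual rate or enrollment period that 192 requires (4.17 a month over 46 months, or 48 months at 4 a month). If the period is extended, show how the nine-month assessment of the last participants fits the project end. If power at 28% attrition is reported, label 66–79% as the result at the maximum attrition over the 3–4 range.

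The cost is text only. Design, analysis and sample-size targets are unchanged; the stated feasibility becomes less favourable, and accrual monitoring gains one consistent benchmark.

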the normal population.²⁰⁶ This criterion is commonly used in assessment of decision-making capacity²¹¹⁻²¹³ and has been shown to be more stringent than expert assessment of capacity.²⁰⁶ Generally, 15 to 20 minutes is required for completion.²¹⁴

As allowed under Virginia state law, an alternative procedure will be used to consent persons lacking the capacity to give informed consent, as determined by the MacCAT-CR or judged by the investigators. Investigators will seek to obtain consent from a legally designated substitute decision-maker. In every case, an effort will be made to obtain assent from the patient. Patients who decline to participate will not be enrolled regardless of their respective substitute decision-maker's desire. Readers should note, the protocol for this project has been submitted for review and approval to the VCU Office of Research Subjects Protection and formal approval is pending. More detailed information regarding human subjects protection and safety monitoring procedures is detailed in the *Human Subjects Narrative* (Form 424) and the *Data and Safety Monitoring Plan*. Readers should also note that, once approved, the study will be registered with ClinicalTrials.gov.

On giving informed consent, participants will be given baseline assessment materials to complete. Estimated time for the completion of baseline measures is 30-40 minutes. Project staff will make accommodations for persons with visual, motor, and other impairments.

Using randomization tables provided by our Biostatistician, [name], participants will be randomly assigned to either of two groups: (1) RAI or (2) RAI+. After randomization, a second appointment will be scheduled. Participants will begin treatment during their second appointment.

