The RAI consists of seven 60-minute sessions scheduled over seven weeks as described in the *Intervention* section. During the first session, participants will receive an empty loose-leaf binder to store and organize completed self-assessments, reading materials, and homework assignments from each session. Participants will also receive a copy of the curriculum, *Getting Better and Better after Brain Injury: A Guide for Survivors, 2nd edition.*¹⁸³ They will be asked to review materials and complete worksheets between sessions. The RAI will be implemented by two experienced, licensed therapists ([name], [name]). Within each treatment condition, participants will be randomly assigned to one of the two therapists. Data will be analyzed to identify any therapist effects.

For the RAI+ participants, three booster sessions will be implemented as described in the

Intervention section of this proposal. The three weekly booster sessions will be scheduled to start

three months following completion of Session VII.

Implementation of quality control procedures: A protocol has been established to ensure the

quality and standardization of treatment implementation across therapists.

During the two-month project start-up period, the therapists ([name], [name]), and [name] will meet to review the manual and discuss implementation and standardization procedures. Following, each therapist will meet with volunteer participants, and implement Session I of the RAI curriculum. Informed written consent for digital audio-recording will be obtained. Afterward, the intervention audio-recordings will be reviewed with [name], with the manual in hand, to make certain that all steps are faithfully completed. Additionally, [name] will assure that therapists have covered the bolded content areas in the manual, which are considered to be key elements of treatment (see Appendix G). Strategies for improving consistency between therapists will be discussed and implemented. Changes will be made in the implementation manual (e.g., clarification of procedures) as needed.

The two therapists will meet again with the same volunteer participants, and implement the remaining six sessions of the RAI curriculum. Again, the audio-recordings will be reviewed with [name], and strategies for adherence to the manual will be discussed and implemented after each session.

Every six months thereafter, the complete quality control procedure will be reapplied.

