Using randomization tables, participants will be assigned to either of two treatment groups: (1) Resilience and Adjustment Intervention (RAI), or (2) RAI+. After randomization, a second appointment will be scheduled. All participants will begin the 7-session treatment during their second appointment. The intervention consists of seven 60-minute sessions scheduled over seven weeks (see attached RAI Implementation Manual). During the first session, participants will receive an empty loose leaf binder to store and organize completed self-assessments, reading materials, and homework assignments from each session. They will be asked to review materials and complete worksheets between sessions. The intervention will be implemented by experienced, licensed therapists (Ph.D. level Interventionists). Participants will be randomly assigned to one of the therapists.

The RAI and RAI+ groups will both complete the post-treatment measures immediately after the seventh treatment session and then 3, 4, and 9 months later. Data collection at 3, 4, and 9 months post-treatment will be completed inperson, unless the participant requests to complete via phone.

Furthermore, the RAI+ group will complete 3 booster sessions, spaced approximately 7-10 days apart, beginning 3 months after completion of the seventh treatment session (booster sessions will occur between the 3 and 4 month data collection described above).

Data will be analyzed to identify any therapist effects, as well as treatment effects. For the RAI and RAI+ groups, demographic, injury severity, and history information will be collected at intake using standard procedures and protocols. All participants will complete the 4 outcome measures (Connor-Davidson Resilience Scale, CD-RISC; Mayo Portland Adaptability Inventory-4, MPAI-4; 13 Item Stress Test; and Brief Symptom Inventory-18, BSI-18) at 5 time points (intake, post-treatment, and 3, 4 and 9 month follow-up).

The RAI is not a standard of care at VCU. Both the RAI and the RAI+ are experimental interventions. Any information collected during the intervention sessions (e.g., questionnaires, lists generated) is part of the experimental intervention, not part of the research data.

7. * The IRB only reviews research activities, so indicate for each of the study activities described in the question above or in the protocol which activities are:

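### Arms are allocated at intake but do not differ until the boosters about five months later, where the primary analysis also starts; allocating, or at least disclosing, at that point would close an avoidable bias route

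*Combined protocol and SAP*

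**What the plan says.** The grant narrative (D6, Procedure) places randomisation after consent and baseline assessment: "After randomization, a second appointment will be scheduled. Participants will begin treatment during their second appointment". The IRB form (Study Procedures, item 6) agrees and makes the common start explicit: "All participants will begin the 7-session treatment during their second appointment". Both arms have seven weekly sessions. Only RAI+ then receives three boosters, "beginning 3 months after completion of the seventh treatment session".

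Outcomes are measured at intake, after Session VII, and 3, 4 and 9 months after that. The primary model (section E, Hypothesis 1) uses the last three: "The model will include fixed-effects for time at RAI+Booster initiation, conclusion, and long-term follow-up (e.g. 5, 6, and 11 months". The covariates are few: "The model will also adjust for fixed-effects for injury severity, time postinjury, and education". The test is on change: "Specific contrast statements will be used to test for a difference in the CD-RISC change scores between the treatment groups", from booster initiation to booster conclusion and from booster initiation to long-term follow-up. CD-RISC at intake and after Session VII is neither a response nor a covariate.

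Section E says the analyses evaluating RAI+ follow intent-to-treat if drop-out is taken to be missing at random or completely at random. It gives no method for participants who have no outcome from month 5 onward.

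**The concern.** Randomisation protects a comparison from the moment of allocation. Here that moment is several months before the treatments differ and before the first score the primary model uses. Two things can happen in between.

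- **Loss.** People who leave for good before the three-month visit are randomised but absent from the analysis. If the arm influences who leaves, the analysed groups are no longer those that were randomised.
- **Expectation and delivery.** If participants or therapists know the arm, a self-rated score at month 5 may already reflect that knowledge, and the shared sessions may be delivered differently.

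The plan's own text makes these routes plausible. Earlier RAI participants asked for a longer programme (Introduction and D3), so assignment to the shorter arm could disappoint. An interventionist may recommend withdrawal for significant distress (IRB form, Risks section, item 5). The same two therapists treat both arms (D6). The month-5 measure is the starting point of both primary contrasts, so it should be free of any effect of allocation.

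**Working it through.** **1. The plan's sample size reproduces.** Inputs (section E): difference 2.9, SD 6.0, 80% power, 0.05 level (two-sided assumed). A two-sample t-test gives 68.2, so 69 per arm, with power 0.805 at 69. Inflation gives 138/(1 − 0.10) = 153.3, or 154 with equal arms (grant narrative), and 138/(1 − 0.28) = 191.7, or 192 (IRB form, Study Population, item 3). None of these figures is disputed.

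**2. Gap between allocation and divergence.** Seven weeks is 49/30.44 = 1.6 months. Adding three months gives about 4.6 months from the start of treatment, which the plan rounds to month 5.

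**3. Who contributes.** A mixed model keeps anyone with at least one modelled response. A participant who misses only month 5 but attends month 6 or 11 stays in. The people lost to the primary analysis are those with none of the three measures.

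**4. How many that could be.** The documents do not divide attrition into before and after month 5, so only a range is possible. The even split is an assumption, taken multiplicatively: early loss = 1 − √(1 − total).

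| Plan | All loss late | Even split | All loss early |
|---|---|---|---|
| 154 at 10% | 0 | 154 × 0.051 = 7.9 | 154 × 0.10 = 15.4 |
| 192 at 28% | 0 | 192 × 0.151 = 29.1 | 192 × 0.28 = 53.8 |

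**5. When this produces bias.** For each arm, let p be the proportion lost before month 5 for good, and D the mean later change of those retained minus that of those lost. The retained mean exceeds the mean of all randomised by p × D. The bias in a change contrast is therefore p(RAI+) × D(RAI+) − p(RAI) × D(RAI). With equal p and equal D it is exactly 0.

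Separately, an effect of knowing the arm on the month-5 score enters the change contrast only so far as it is not carried through to month 6 or 11. A shift that persists cancels, and one that fades does not. The documents supply neither p nor D by arm, nor the size of any such shift. Neither the size nor the direction of bias can be computed.

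**6. What late randomisation does to numbers.** The evaluable target stays 138. At 28% total attrition, enrolment is 192 to 194 and the number randomised is 138 to 192, depending on the split. At 10%, enrolment is 154 to 155 and the number randomised is 138 to 154.

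**The case against.** **Disclosure is inferred.** No section says that participants or therapists are told the arm at intake. The consent form and implementation manual are listed but not available to the reader. This stands: one can say that knowledge of the arm could matter, not that it does.

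**Loss alone is harmless if balanced.** Correct. Equal and similar loss costs precision and some generalisability, and the inflation to 192 covers the numbers.

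**Deferral of content is limited.** Session topics are fixed, and audio review checks key content every six months. This narrows the delivery route. However, the seven-session review uses volunteers' recordings, so it is only partial protection against delivery that differs by arm.

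**Intake randomisation is legitimate** for comparing whole programmes, and it gives a pre-treatment baseline. That is so, but the primary model does not use that baseline.

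**A cheaper repair exists.** The intake and post-treatment scores could enter the model for all randomised participants. That would help with the intent-to-treat label but would leave the expectation route open.

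**A reader might infer a bias size.** Suppose 20% early loss in RAI and 10% in RAI+, with leavers half an SD lower (half of the 7.8 follow-up SD in the earlier trial's table, 3.9). The arms would then differ by 0.10 × 3.9 = 0.39 points at month 5, or 13% of 2.9. The documents do not support that figure. The loss rates and the half SD are invented, and 0.39 is a gap in level while the target is a difference in change. If the gap acted only through regression to the mean, with equal SDs at both visits, the slope would be (change SD)²/(2 × 7.8²). That is 25/121.7 = 0.21 to 36/121.7 = 0.30 for change SDs of 5.0 to 6.0. The effect on the contrast would be about 0.08 to 0.12 points, 3 to 4% of 2.9.

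**Conclusion.** The point holds as an avoidable weakness in design. Allocation precedes any difference in treatment by about 4.6 months from the first session, the primary comparison begins only then, and nothing available keeps the arm undisclosed in between. The intent-to-treat label does not by itself protect a comparison that omits randomised participants with no later measure.

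The size is a range of people: 0 to about 15 of 154, or 0 to about 54 of 192. It is not a number of CD-RISC points. A reader might conclude that the primary result will be biased. That would require loss or shared-phase response to differ by arm, which the documents neither show nor exclude. The change is worth making because it is cheap and the plan gives no reason for allocating early.

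**What to change.** Either of two changes would do.

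1. **Randomise later.** Allocate to RAI or RAI+ after the three-month post-RAI measures are complete. Assign the therapist at intake and randomise arm within therapist. The month-5 score then becomes a true pre-randomisation baseline.
2. **Keep intake randomisation but conceal it.** The biostatistician holds the table and releases each assignment to participant, interventionist and assessor only after those measures. With identical treatment and no one aware of the arm, earlier loss cannot depend on it.

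Section E should also state how randomised participants with no measure from month 5 onward are handled, and loss before that visit should be reported by arm.

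**Cost.** Consent and procedure wording change. D6 assigns therapists within treatment condition, so that order must be reversed under option 1. Under option 2 the therapist must be released without revealing the arm. Booster appointments can be booked only after the three-month measures. Under option 1 the randomised population becomes those who return at three months, nearly the same people the primary model can use, and total enrolment hardly moves.
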